4.0 Study Endpoints

Outcomes will include vital signs, and ratings of anxiety, pain, and stress. Over the course of the study visit, physiological measures will be collected before, during, and after a cold pressor test (more about data collection below). Visual analog measures of anxiety, stress, and pain will be collected throughout each study visit.

Primary Outcome:

Given that safety and feasibility of taVNS and this intervention have already been established by prior studies, the primary outcomes in this study will be the physiological measures collected at each study visit (Badran, 2019). Both taVNS and the validated cold pressor test have been shown to be safe and feasible in neurotypical subjects (Badran 2018a, b, c; Lovallo, 1975). Biopac equipment will be used to continuously measure heart rate/variability (HRV) and blood pressure to assess autonomic responses.

Secondary Outcome:

Subjective measures of pain, stress, and anxiety will also be collected before, during, and after the cold pressor test (with concurrent taVNS). These will be measured using visual analog scales. Baseline measures of anxiety and mood will also be collected at the initial visit.

5.0 Inclusion and Exclusion Criteria/ Study Population

This study seeks to recruit from a broad range of individuals in order to ensure generalizability, though some exclusion criteria are necessary to ensure participant safety. Participants will call the lab and complete a phone screener which assesses for the following criteria. The recruited sample will be 50% female. No racial or ethnic groups will be excluded during recruitment, nor will any other individuals with diverse backgrounds. However, participants must be English speaking, as the study consent and other tasks are presented in the English language. Risks of taVNS to a fetus are currently unknown. Thus, women of childbearing age will be screened for pregnancy during the phone screener and will be provided a pregnancy test prior to stimulation to confirm they are not pregnant.

Inclusion Criteria

- Ages 18-65 years
- English speaking
- Non-treatment-seeking community members

Exclusion Criteria

- Diagnosis of COVID-19 in the past 14 days
- Facial or ear pain or recent ear trauma.
- Metal implant devices in the head, heart or neck.
- History of brain stimulation or other brain surgery.
- History of myocardial infarction or arrhythmia, bradycardia.
- Use of B-blockers, antiarrhythmic medication (sodium/potassium/calcium-channel blockers), or blood pressure medications.

- Active respiratory disorder.
- Personal or family history of seizure or epilepsy or personal use of medications that substantially reduce seizure threshold (e.g., olanzapine, chlorpromazine, lithium).
- Personal history of head injury, concussion, or self-report of moderate to severe traumatic brain injury.
- Individuals suffering from frequent/severe headaches.
- Individuals with a reported history of any mental health disorder or taking any psychotropic medications.
- Moderate to severe alcohol or substance use disorder.
- Pregnancy

6.0 Number of Subjects

We will recruit 24 adults in order to have at least 14 completers.

7.0 Setting

All participants will complete the study tasks in a dedicated research suite, the Psychophysiology Center, in the Brain Sciences Department. The space to be used here is currently assigned to researchers on this study team and is well equipped for stimulus-controlled physiological recording. In addition, this space is used only for research protocols and thus is accessed at limited times. Studies assigned to this space may only enter during their assigned hours to ensure participant confidentiality and privacy. This also ensures COVID-19 related precautions may be taken: limiting use of space to no more than the participant and the study researcher and allowing time between participants for cleaning/sanitation, requiring the use of masks for researchers and participants.

8.0 Recruitment Methods

Participants will be recruited from the Charleston community. Potential participants will be recruited via flyers (see advertisements) placed at approved sites at MUSC's library and hospital, as well as within the IOP. Appropriate approvals will be received prior to posting flyers.

When a potential participant contacts about the study, trained research assistants will overview all procedures and specify the expected duration and compensation. The PI and Co-I will train staff in answering questions related to study procedures. After providing information about the study, a phone screener will be completed. Participants will be asked to complete this portion in a private setting. Should participants meet the inclusion/exclusion criteria and they agree participate, subjects will be provided with available participation dates. They will also be provided with instructions on how to locate the lab space. Participants will be asked to refrain from alcohol use and intense physical activity 24 hours before the study, as well as refrain from caffeine 6 hours and tobacco 2 hours prior to the study. Participants will be encouraged to sleep as they usually do the night before the study.

9.0 Consent Process

The consent form will be provided to participants at the in-person visit. Participants will be given ample time to read the consent form and a researcher will describe the content of the consent form to ensure understanding, including describing the laboratory measures, study duration, and equipment and materials. The researcher will describe confidentiality/privacy measures, participant right to withdraw, risks/benefits, and compensation. In addition, participants will be prompted to ask questions throughout consenting to further ensure understanding. After signing the consent form, they will also be offered a hard copy which will be provided during the in-lab scheduled participation date.

[figure not shown]
10.0 Study Design / Method

After completing the phone screener, participants will be invited to in-lab participation for 1 visit: they will be provided available times and instructed on how to locate the laboratory space. They will be asked to refrain from the following prior to the study: Tobacco use within 2 hours, Caffeine within 6 hours, Alcohol within 24 hours, and intense physical activity within 24 hours. Participants will be asked to sleep as they usually do the night before the study.

Prior to arrival to the research space, after phone screening, participants will be consented at the in-person visit (see Section 9.0). Subjects will present to the laboratory for 1 visit. Once participants have arrived in the laboratory for the visit, if they are a woman of childbearing age, they will be provided with a pregnancy test strip to take in privacy. They will be provided instructions on how to use the test, as well. After completing the pregnancy test, participants with negative results will be asked to continue to the remaining study procedures, whereas those with a positive result will be debriefed, compensated for their time, and released.

During the laboratory visit, subjects will twice participate in a validated stress induction technique known as the Cold Pressor Test (CPT) while concurrently receiving either active or sham transcutaneous auricular vagus nerve stimulation (taVNS). Over the course of 2 cold pressor tests, subjects will receive both stimulation conditions (half will be randomized to receive active stimulation first and half will receive sham stimulation first). Physiologic measures will be collected before, during, and after each CPT, and there will be a resting period of at least 25 minutes between each CPT. Subjective measures of anxiety, stress, and pain will also be collected throughout the procedure. See Figure 2 for a timeline of the study visit's course.

Figure 2. Study visit timeline (for participant randomized to receive active taVNS first)

Timeline consists of 2 cold pressor tests (CPT) and 2 stimulation conditions (active and sham). The cold pressor test (CPT) will last for up to 3 minutes. Subjects will receive either active or sham taVNS for up to 5 minutes (stimulation will start prior to CPT and continue throughout the duration of the CPT). The order in which participants receive active or sham taVNS will be randomized, but all participants will receive both treatment conditions. Physiologic data will be continuously measured throughout the course of each visit.

Cold Pressor Test: The CPT was first introduced in the 1930s by Hines and Brown (Hines, 1932). CPT exposure leads to profound changes in cardiovascular parameters most notably a rise in blood pressure throughout peripheral vasoconstriction and to a lesser extent cardiac output resulting from an increase in both vascular alpha-adrenergic and cardiac beta-adrenergic drive (Greene et al., 1965; Lollo, 1975; Yamamoto et al., 1992). On the subjective level participants experience the CPT as painful and report heightened levels of perceived stress and arousal during and immediately after the water-bath (Zoladz et al., 2014). A plethora of research has contributed to the validation and standardization of the CPT.

Prior studies have shown an enhanced response, in terms of sympathetic parameters, to a bilateral feet CPT (Larra, 2015). This is what will be used in this trial. As in previous studies (Larra, 2015; Bachman, 2018), the CPT will consist of participants immersing both feet into ice-water (water temperature around 2-3 degrees Celsius) for up to 3 minutes. The water-bath will be a rectangular tub with ample volume to submerge the subject's feet completely with ice-water.

Upon arrival, subjects will be asked to sit comfortably in a chair as electrodes are applied to collect physiological data (see physiology section below). The protocol will start with a resting period during which heart rate and blood pressure will be assessed. Subjects will receive a 2-minute warning prior to the start of the CPT. Subjects will be asked to rate subjective anxiety, stress, and pain during this resting period. After the resting period, subjects will be exposed to the CPT for up to 3 minutes. During the exposure to the ice water, subjects will again rate subjective anxiety, stress, and pain. The stress procedure will be followed by another resting period, during which heart rate and blood pressure will continue to be monitored. Again, participants will rate subjective anxiety, stress, and pain.

taVNS: The taVNS stimulation administered during the study *is non-invasive but includes some risk*. Participants will be screened for potential contraindications to taVNS prior to invitation to the lab (see Section 5.0 for exclusion criteria; e.g., ear trauma/pain, metal implants). The device has safety mechanisms to prevent electrical surges. Skin will be prepared using 70% alcohol swabs prior to electrode attachment to ensure sanitation and stimulation power is safe. Metal jewelry also will be removed from the head. Stimulation is applied using electrodes and a water based conductive gel, and participants will be assessed after application/prior to stimulation for discomfort related to the electrode. Participants will be assessed during stimulation for discomfort or adverse events over the course of stimulation, though

studies have demonstrated few concerns of safety. Participants are encouraged to share report of discomfort and are reminded prior to the study they may discontinue at any point. The ear also will be cleaned and inspected for irritation/redness after stimulation. The ear stimulation delivered during the study includes some risk. Participants in previous research using this stimulation describe the feeling as a “tickle” or “pricking” sensation. Some report mild irritation. Our researchers will inspect the ear after stimulation given previous research has documented some redness from the stimulation.

Physiology: For sensors that are attached to skin there is some risk for mild local irritation or redness, thus adhesives are removed with caution/gently.

Confidentiality: To protect confidentiality of study-specific measures, only the participant code, and no potentially identifying information (e.g., name, date of birth) will ever be associated with these measures. In addition, self-report data will not include identifiable information. Self-report data are in Likert format and will be linked only to a participant code. Thus, no data will be identifiable. However, there is still a small risk of loss of confidentiality of participant information in this study. Steps taken to protect confidentiality are described further in the **Data Management** section.

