1.0 Objectives / Specific Aims

Aim 1. Assess whether the parasympathetic effects of transcutaneous auricular vagus nerve stimulation (taVNS) are able to attenuate the sympathetic response curve elicited by a validated cold pressor test.

We will recruit 24 neurotypical subjects (ages 18-65) in order to have at least 14 completers. The subjects must be at baseline healthy, and not have a history of major mental or medical illness (see more below for full inclusion/exclusion criteria). Each subject will undergo phone screen and be consented prior to participating in the study. Each subject will participate in 1 study visit, where they will participate twice in the validated cold pressor test while concurrently receiving active or sham taVNS. Subjects will participate in both treatment conditions (active and sham taVNS), however the order in which they participate will be randomized (half will receive active taVNS first, half will receive sham first). The cold pressor test is a validated stress induction technique and has been shown to produce a reliable sympathetic response, as shown by acute elevations in sympathetic physiologic markers (heart rate, blood pressure/mean arterial pressure, cardiac output, etc). In prior studies, taVNS has been shown to produce a marked and significant parasympathetic response in neurotypical subjects, shown by acute reductions in the same markers as above. Both taVNS and the validated cold pressor test have been shown to be safe and feasible in neurotypical subjects. We hypothesize that subjects receiving active taVNS will have an attenuated sympathetic response to the cold pressor test compared to those receiving sham stimulation.

Aim 2. Assess whether taVNS affects the subjective pain/stress response to a validated cold pressor test.

Subjects will be asked to rate subjective pain and stress before, during, and after the cold pressor test. We hypothesize that these subjective ratings will be reduced in the group receiving active taVNS compared to the sham group.

Aim 3. Assess the acute effects of transcutaneous auricular vagus nerve stimulation (taVNS) on anxiety.

In other pilot trials using taVNS, as well as past trials with implanted VNS, results have shown taVNS and implanted VNS to have an anxiolytic effect. We hypothesize that taVNS will have a similar anxiolytic effect on subjects in this trial. This work will provide pilot data for subsequent studies to investigate the anxiolytic effects of taVNS.

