3.0 Intervention to be studied

The intervention we are studying is called transcutaneous auricular vagus nerve stimulation (taVNS). taVNS is simply electrical nerve stimulation administered at the ear which targets the auricular branch of the vagus nerve. taVNS will be administered using the Digitimer DS7a nerve stimulation system that has an FDA 510k approval. taVNS is a non-significant risk method that has been approved by the MUSC IRB for many ongoing taVNS trials.

The Digitimer DS7a manual has been uploaded the MUSC IRB portal and can be found here: <https://www.digitimer.com/product/human-neurophysiology/peripheral-stimulators/ds7a-ds7ah-hv-current-stimulator/>

- Cervical VNS is FDA approved for medication resistant epilepsy as well as medication resistant depression (Livanova). FDA pivotal trials are underway for paired cervical VNS with rehab for stroke (microtransponder). Noninvasive cervical VNS is FDA approved for treating cluster headache (electrocore). To date there are no FDA approved indications for taVNS.
- We will use the device during each study visit for up to 5 minutes while subjects concurrently participate in the cold pressor test. Subjects will receive both stimulation conditions over the course of the study visit (active taVNS x1, sham taVNS x1). Subjects will be blinded to stimulation condition, but the research team will know whether patients are receiving active or sham stimulation. The order in which subjects receive either active or sham stimulation will be randomized (half will receive active taVNS first, half will receive sham taVNS first).

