14.0 Withdrawal of Subjects

Participants will be informed during consenting that they are free to withdraw from the study at any time. They will be informed that they are not obligated to participate once the study is initiated and in particular will be reminded prior to taVNS/VNS stimulation they may discontinue stimulation and/or the experiment at any point.

Study advertisements will not state the amount of compensation to be provided, so as to prevent potential subjects from participating out of need. Study personnel will not pressure any participant to engage in the study or in parts of the study. Research personnel may choose to end participation early if the subject appears or expresses distress by the study procedures.

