15.0 Risks to Subjects

Physiology: The study procedures may involve non-invasive recording of EMG and ECG, so the risk with this is minimal. For external sensors used for ECG and EMG, adhesive disks are used. Removal of these adhesives may result in mild local irritation or redness.

Ear Stimulation: Ear stimulation is safe, however there are some risks associated with stimulating the ear: There may be local discomfort. This will likely be temporary. In extreme cases burns might occur. We will video monitor any potential burns and will stop stimulation and advise subjects to apply vitamin E cream. Tissue surrounding the ear may be sensitive, sore or feel slight numbness. Hopefully this will be temporary and will go away after stimulation is turned off.

Potential Headache, Dizziness, and Facial Pain: Ear stimulation might cause headaches or face pain, which should resolve shortly after treatment.

Safety in case of pregnancy: This protocol will exclude pregnant women. The risks of using taVNS with pregnant women are currently unknown. If in the screening and consent a patient is a woman of childbearing age, a urine pregnancy test will be completed.

Cold Pressor Test: Prior studies have shown the safety and feasibility of the cold pressor test in neurotypical populations. Subject's discomfort will be monitored closely and throughout the test. Previous studies have shown that neurotypical participants are able to tolerate and complete the cold pressor test without residual discomfort following the test. Subjects will have the option to withdraw at any time throughout the test if discomfort is too great or per their preference. Of note, active taVNS is hypothesized to attenuate the sympathetic response to the cold pressor test. Thus, one out of the two cold pressor tests may have a higher risk of discomfort (subjects will receive active and sham taVNS in randomized order).

Risk of Increased/Decreased Heart Rate: The Cold Pressor Test is associated with an acutely elevated heart rate. Other studies have shown the safety and feasibility of this technique, and elevations in heart rate have been shown to stay within the normal range of physiologic functioning. taVNS is also associated with decreases in heart rate. The safety and feasibility of taVNS has also been shown by prior studies. Study staff will closely monitor changes in heart rate, as well as patient's comfort levels, and will respond to changes accordingly.

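### Does a cold pressor immersion of variable length, with completer undefined and immersion time not a listed outcome, call for a protocol change?

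*Protocol*

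**What the plan says.** The timeline in Section 10.0 gives the immersion a maximum and no minimum: "The cold pressor test (CPT) will last for up to 3 minutes". Section 15.0 lets subjects stop: "Subjects will have the option to withdraw at any time throughout the test if discomfort is too great or per their preference". The same paragraph notes that active stimulation is hypothesized to blunt the response and concludes: "Thus, one out of the two cold pressor tests may have a higher risk of discomfort". It also reports that "Previous studies have shown that neurotypical participants are able to tolerate and complete the cold pressor test".

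Section 14.0 adds a staff decision: "Research personnel may choose to end participation early if the subject appears or expresses distress by the study procedures". Section 3.0 states that "the research team will know whether patients are receiving active or sham stimulation".

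The target appears twice, in Section 1.0 ("We will recruit 24 neurotypical subjects (ages 18-65) in order to have at least 14 completers") and in Section 6.0 ("We will recruit 24 adults in order to have at least 14 completers"). Neither place defines a completer. Section 4.0 names physiological measures as primary and visual analog ratings as secondary; time in the water is not among them.

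**The concern.** In a two-period crossover the active and sham tests should deliver the same stressor. Here the length of the stressor can vary, and the protocol itself gives a reason why it might vary with the condition: if sham hurts more, subjects may leave the sham bath sooner. Staff who know the condition may also act on apparent distress.

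Two consequences seem possible. If early leavers do not count as completers, the 14 are partly chosen by how well they tolerate both baths, and the result describes a hardier group. If early leavers do count, mean cold exposure may differ between active and sham, and a reader without immersion times could not judge by how much. Because completer is undefined, it is unclear which case applies. An allowance of 10 losses in a single-visit study makes the question look larger.

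**Working it through.** **Inputs.** From the protocol: 24 recruited and at least 14 completers (Sections 1.0 and 6.0); a ceiling of 3 min = 180 s (Section 10.0). The protocol gives no significance level, power, effect size or expected loss rate, so neither 24 nor 14 can be reproduced. Only the implied allowance can. All exit rates, exit times and correlations below are assumptions.

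**Step 1: the allowance.** 24 − 14 = 10, and 10/24 = 41.7%. If all ten were early exits, equally likely and independent in the two tests, then (1 − p)² = 14/24, so p = 1 − √0.583 = 23.6% per test. If the same subjects left both baths, p = 41.7%. These are upper limits, because other losses draw on the same ten. For example, consent is taken only at the visit (Section 9.0), and subjects with a positive pregnancy test are released (Section 10.0).

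**Step 2: does the definition decide whether 14 is reached?** Suppose a completer needed two full 3-minute immersions, a rule the protocol does not state. With independent exits, the expected number is 24 × (1 − p_sham) × (1 − p_active).

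| Assumed exit, sham / active | Expected with two full immersions | P(at least 14) |
|---|---|---|
| 10% / 5% | 24 × 0.90 × 0.95 = 20.5 | above 0.99 |
| 20% / 10% | 24 × 0.80 × 0.90 = 17.3 | 0.95 |
| 30% / 15% | 24 × 0.70 × 0.85 = 14.3 | 0.63 |
| 40% / 20% | 24 × 0.60 × 0.80 = 11.5 | 0.21 |

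If early leavers count, none is lost for this reason. The definition matters only at high exit rates.

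**Step 3: selection, if early leavers were dropped.** Suppose the most exit-prone subjects are exactly the ones lost, on a normal trait, with share q kept. The mean shift is −φ(z_q)/q. For q = 14/24, z = 0.210 and the shift is −0.67 SD. For q = 19/24, z = 0.812 and the shift is −0.36 SD. With no such losses it is 0. With an assumed correlation of 0.3 to 0.5 between the trait and the pressor response, the first becomes 0.20 to 0.33 SD and the second 0.11 to 0.18 SD. All of this presupposes that only completers are analysed, which the protocol does not say. Even then each subject remains their own control.

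**Step 4: exposure, if early leavers were kept.** Suppose k of 24 subjects leave at 90 s in the sham test only. The mean sham deficit is k/24 × (180 − 90) s: 37.5 s for k = 10, 18.75 s for k = 5, 7.5 s for k = 2, and 0 if exits are balanced. The value k = 10 has no basis here, because it borrows the loss allowance while treating these subjects as not lost. For a response present only during immersion and averaged over a fixed 3-minute window, each extra 10 percentage points of sham tests ended at 90 s lowers the sham mean by 0.10 × 0.5 = 5%. That pulls the contrast towards no effect, against the trial's hypothesis. The direction reverses if exits are commoner under active.

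**Step 5: the passages side by side.**
- Sections 1.0 and 6.0 fix recruitment at 24. Fourteen is a minimum yield, and nothing stops enrolment when it is reached.
- Sections 10.0 and 15.0 agree: a maximum time leaves room for an option to stop. Section 15.0 is a risk statement and not a rule for classifying subjects.
- Section 10.0 describes a visit made of two tests, with every subject receiving both conditions. The ordinary reading of completer is someone who did both.
- Section 14.0 concerns ending participation altogether, not shortening one bath. A subject removed before the second test has no pair under any definition.
- Section 4.0 lists outcomes. Immersion time is a record of exposure, and its absence there does not mean it goes unrecorded. Section 10.0 provides for continuous physiological recording throughout the visit.

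**The case for a change.** The strongest case for a change is about data capture. Continuous recording may show when the feet left the water, but not who ended the test or why, and no analysis plan can recover a reason that was not noted on the day. A definition of completer settled after exits have been seen is also open to choice. And if leaving the first bath were treated as leaving the study, the second condition would never be given and the pair would be lost.

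Part of this stands. Noting the stop time and reason is good practice, and the protocol does say that discomfort may differ between the two tests. But it is case-report-form detail, and its absence from an outcome list is not an error. The fear of a convenient definition carries little weight, because the protocol attaches neither a stopping point for recruitment nor an analysis set to the count of 14. Whether a subject went on to the second test will be plain from the data, whatever label is used. How short immersions enter the analysis, including the choice of window, is ordinarily left to the statistical analysis plan, which is not at hand.

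**Conclusion.** No change is needed. The observations are correct as far as they go: immersion time can vary, early exit could depend on condition, and completer is undefined. None of them contradicts another statement in the protocol or makes a stated number or rule wrong, and writing the definition down would alter no result. This is a gap that analysts fill sensibly, by taking subjects with data from both tests and describing immersion times.

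The size is unknown. The figures of 0.67 SD and 37.5 s are ends of assumed scenarios, not estimates; every such range includes zero, and Section 15.0 suggests that early exits will be few. The conclusion rests on reading 24 as the recruitment number and 14 as a floor, and on the absence of any stated completers-only analysis. If an analysis plan restricted the analysis to full immersions, the question of whom the result describes would have to be taken up there.

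### Does it matter that the text does not say whether the rating before the cold pressor test comes before or after stimulation starts?

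*Protocol*

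**What the plan says.** Three parts of the protocol bear on the timing.

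- **Section 3.0 (Intervention to be studied)** gives the device time: "We will use the device during each study visit for up to 5 minutes while subjects concurrently participate in the cold pressor test". It gives no onset. It adds that each participant receives one active and one sham application, and that participants are blinded but "the research team will know whether patients are receiving active or sham stimulation".
- **Section 10.0, the text describing the Figure 2 timeline**, gives a CPT length ("The cold pressor test (CPT) will last for up to 3 minutes"), a stimulation length ("Subjects will receive either active or sham taVNS for up to 5 minutes") and the relation between them: "stimulation will start prior to CPT and continue throughout the duration of the CPT".
- **Section 10.0, the Cold Pressor Test procedure**, gives the order of events: a first rest with heart rate and blood pressure assessed, then immersion, then a second rest. Within the first rest, "Subjects will receive a 2-minute warning prior to the start of the CPT", and "Subjects will be asked to rate subjective anxiety, stress, and pain during this resting period". Then: "After the resting period, subjects will be exposed to the CPT for up to 3 minutes". Ratings are repeated in the water and in the second rest. Stimulation is not mentioned in this sequence; it has its own paragraph.

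Section 4.0 makes the continuously recorded physiology primary and the visual analog ratings secondary. It ties the ratings to the CPT, not to the start of stimulation. Section 10.0 refers the reader to Figure 2 for the course of the visit.

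**The concern.** If stimulation begins before the CPT, and the CPT begins when the rest ends, then some stimulation falls inside the rest in which the first rating is taken. The text does not say on which side of stimulation onset that rating lies.

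The two possibilities mean different things. Before onset, the rating is a clean baseline for that CPT. After onset, it already contains any effect of stimulation alone, and subtracting it could remove part of the effect that Aims 2 and 3 look for. Physiology can be re-windowed afterwards because it is recorded throughout; a rating cannot be moved once taken. Because the staff know the condition, one might also worry that the moment of rating could drift between active and sham.

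A second oddity adds to the impression of inconsistency. Section 3.0 reads as a limit of 5 minutes for the visit, and as use only during the CPT, while Section 10.0 has a lead-in and two applications.

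**Working it through.** The protocol gives no figure to reproduce here. The check is a comparison of texts with a little arithmetic on the stated maxima.

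**1. Do the sections place stimulation differently?**

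| Source | Onset | Duration |
|---|---|---|
| Section 3.0 | not given; use is concurrent with the CPT | up to 5 min |
| Section 10.0, timeline text | before the CPT, continuing through it | up to 5 min |
| Section 10.0, CPT procedure | stimulation not mentioned | CPT up to 3 min |

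Only one source states an onset. Section 3.0 does not confine stimulation to immersion, and 5 minutes cannot lie wholly inside a CPT of at most 3. The CPT procedure is silent, which is not a competing placement. All three fit one timeline.

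**2. How long is the lead-in?** If both maxima apply and stimulation ends with the CPT:

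- lead-in = 5 - 3 = 2 min per condition;
- share of stimulation time = 2 / 5 = 40%.

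Both inputs are upper limits, so 2 minutes is the value at the maxima and not a protocol figure. It equals the 2-minute warning, but the text does not link the two.

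**3. What does the order of rating and onset change?** Write *d* for the effect of active versus sham on the rating in the water, and *p* for the corresponding effect on the rating in the first rest.

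- Comparing the in-water ratings directly, active minus sham within participant, estimates *d* in either order.
- Comparing changes from the first rating estimates *d* - *p*. If the rating precedes onset, that application cannot yet have acted, so *p* = 0 and the change also estimates *d*. If it follows onset, *p* may differ from 0 and the change has another meaning.

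So the order affects the interpretation of a change score, not the validity of the comparison, provided the rating is taken at the same point under active and sham. Section 10.0 describes one procedure and does not vary it by condition.

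**4. Stimulation time per visit.**

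- Section 3.0 read as a per-visit limit: up to 5 min.
- Section 10.0 with two conditions in the one visit: up to 2 x 5 = 10 min.
- Stimulation throughout two full CPTs, with no lead-in: 2 x 3 = 6 min, already above 5.

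This comparison assumes that sham counts as device use, which the available text does not define. It says nothing about when ratings are taken.

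**The case for a change.** The strongest case for a change is that the timing of a rating is trial conduct, which Section 10.0 sets out to describe, so it is not something to leave to an analysis plan. Stimulation is itself felt: Section 10.0 reports tickling or pricking, and Section 13.0 quotes mean pain ratings of 2.1 and 1.2 out of 10 at two ear sites in earlier work. A pain rating taken in the lead-in could therefore include pain from the electrode; one taken before onset could not. The lead-in is also the only described period of stimulation without cold water, which gives it some interest for Aim 3. A sentence would settle the matter at almost no cost.

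Part of this stands. No sentence in the running text ties the first rating to stimulation onset, and the per-visit wording in Section 3.0 does not sit well beside Section 10.0. But the argument shows that the rating can mean two things, not that the comparison fails under either. Harm requires the moment to differ between conditions, and nothing in the protocol suggests that; knowledge of the condition among staff is not evidence of it. The gap may also not exist in the full protocol, since Figure 2 is where the order would be expected and its absence here is a matter of extraction. A further rating at the end of the lead-in would be a preference, and the choice of a physiological baseline window can reasonably be left to the analysis plan.

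**Conclusion.** No change to the plan is needed. Sections 3.0 and 10.0 do not give conflicting placements of stimulation: one states an onset before the CPT, and the others are compatible with it. What remains is a detail that the running text leaves open, concerning a lead-in of about 2 minutes at the stated maxima and a secondary outcome only. Those running the visits will know the order, and an analyst who learns it can compare the in-water ratings directly or read a change score accordingly.

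This rests on two assumptions: the rating is taken at the same point under active and sham, as the single described procedure implies, and Figure 2 does not contradict the text.

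The difference between 5 minutes per visit and up to 10 minutes over two conditions is a slip of wording if sham counts as device use. The two sections should be reconciled when the text is next tidied, and which duration applies is for the study team. It alters neither the design nor the validity of the active-sham comparison. No bias or loss of power has been shown.
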